8.4 Treatment Compliance

Treatment compliance will be assessed via compliance with scheduled weekly infusions.

9 STUDY VISITS

The schedule outlining the study assessments and times of assessments is shown in Section 9.9 and all procedures are described in detail in Section 10. **All assessments scheduled on the same day as study treatment administration are to be completed prior to initiation of study treatment infusion.**

9.1 Screening and Baseline (Approximately 8 weeks prior to Week 1)

9.1.1 Informed Consent

Subjects and/or parent(s)/legal guardian(s) will be invited to review and sign the Informed Consent Form (ICF) and assent (if applicable) to participate in this trial prior to the collection of any data and any study related procedures. Overall study requirements and details surrounding Screening and Baseline assessments are reviewed by the subject and their parent(s)/guardian(s) during this process. Baseline measures from subjects will be obtained prior to infusion.

If there are changes to the study that affect the consent or assent, parents and or the subject will be re-consent/assented at their next visit.

9.1.2 Screening

The screening evaluations will take place over two visits to allow time for assessment of all available criteria before the subject undergoes sedation.

9.1.2.1 Screening Day 1

The following assessments will occur at this visit:

- Informed Consent
- Assent, if applicable
- Medical history
- Concomitant Medications
- Full Physical Exam
- Vital Signs
- Weight

The following blood lab work will occur at this visit:

- Hepatitis B, C and HIV
- Complete Metabolic Panel (CMP)
- Amylase
- Gamma-glutamyl transpeptidase (GGT)
- Complete Blood Count (CBC)/Differential
- Coagulation Measures
- Uric Acid
- Lactate dehydrogenase (LDH)
- C-reactive Protein (CRP)
- Creatine Kinase (CK)
- Cystatin C
- Genotyping of *DMD*, if not previously done

The following urine lab work will occur at this visit:

- Urinalysis

9.1.2.2 Screening Day 2

The following will be assessed at this visit:

- Adverse Events
- Concomitant Medications
- ECHO
- ECG
- Bayley scale of Infant Development (6 to 36 months of age)
- 100M – ambulant subjects (3.5 years until non-ambulant)
- NSAA (3 years to non-ambulant)
- Active-seated – non ambulant subjects (5 years and older)
- Pulmonary functional test (PFT) (10 years and older)
- Timed functional tests for (ambulant subjects 3 years and older)
- Pediatric Outcomes Data Collection Instruments (PODCI, ages 2-17)
- Patient-Reported Outcomes Measurement Information System (PROMIS) Upper Extremity Report (ages 18+)
- Assessment of inclusion and exclusion criteria
- Height

9.1.3 Baseline

The baseline visit should occur 3-5 weeks after screening is completed and will occur over two days.

9.1.3.1 Day 1

The following assessments will occur at this visit:

- **Confirmation of eligibility**
- Medical history
- Adverse Events
- Concomitant Medications
- Full Physical Exam
- Vital Signs
- Height
- Weight
- ECG
- Bayley scale of Infant Development (6 to 36 months of age)
- 100M – ambulant subjects (3.5 years until non-ambulant)
- NSAA (3 years to non-ambulant)
- Active-seated – non ambulant subjects (5 years and older)
- Pulmonary functional test (PFT) (10 years and older)
- Timed functional tests for (ambulant subjects 3 years and older)
- Pediatric Outcomes Data Collection Instruments (PODCI, ages 2-17)
- Patient-Reported Outcomes Measurement Information System (PROMIS) Upper Extremity

Report (ages 18+)

The following blood lab work will occur at this visit:

- Complete Metabolic Panel (CMP)
- Amylase
- Gamma-glutamyl transpeptidase (GGT)
- Complete Blood Count (CBC)/Differential
- Coagulation Measures
- Uric Acid
- Lactate dehydrogenase (LDH)
- C-reactive Protein (CRP)
- Creatine Kinase (CK)
- Cystatin C

The following urine lab work will occur at this visit:

- Urinalysis

9.1.3.2 Day 2

A baseline open muscle biopsy will be performed in one gastrocnemius muscle or alternate muscle. (Note that the rationale and methods of muscle biopsy site selection and performance for this and subsequent biopsies are discussed in Section 10.2.1). If in the discretion of the principal investigator, an implanted venous access port needs to be placed prior to infusion, this placement may occur at the same time as the muscle biopsy. RNAseq analysis will be completed on tissue from this muscle biopsy.

If in the opinion of the Principal Investigator, a PORT placement is indicated, all attempts will be made to have this occur during this same sedation event (see Section 8.2 for full details), but if it is not feasible, a separate visit will be scheduled to place the port.

9.2 Week 1

Week 1 should occur within 4 weeks of the Baseline Functional Assessment Visit. If the Week 1 visit is > 4 weeks after Baseline, the subject is required to repeat the Baseline functional assessments to reconfirm eligibility.

Infusion with the study drug will begin at Week 1 and will occur weekly through the week 48 visit. For details regarding the infusion, please see Section 8.2.

The following assessments will occur at this visit:

- **Confirmation of eligibility**
- Medical history
- Adverse Events
- Concomitant Medications
- Full Physical Exam
- Vital Signs
- Weight

- Infusion

The following blood lab work will occur at this visit:

- Complete Metabolic Panel (CMP)
- Amylase
- Gamma-glutamyl transpeptidase (GGT)
- Complete Blood Count (CBC)/Differential
- Coagulation Measures
- Uric Acid
- Lactate dehydrogenase (LDH)
- C-reactive Protein (CRP)
- Creatine Kinase (CK)
- Cystatin C

The following urine lab work will occur at this visit:

- Urinalysis

9.3 Week 4 (+/- 1 week)

The following assessments will occur at this visit:

- Medical history
- Adverse Events
- Concomitant Medications
- Full Physical Exam
- Vital Signs
- Weight
- Infusion

The following blood lab work will occur at this visit:

- Complete Metabolic Panel (CMP)
- Amylase
- Gamma-glutamyl transpeptidase (GGT)
- Complete Blood Count (CBC)/Differential
- Coagulation Measures
- Uric Acid
- Lactate dehydrogenase (LDH)
- C-reactive Protein (CRP)
- Creatine Kinase (CK)
- Cystatin C

The following urine lab work will occur at this visit:

- Urinalysis

9.4 Week 8 (+/- 1 week)

The following assessments will occur at this visit:

- Medical history
- Adverse Events
- Concomitant Medications
- Brief Physical Exam
- Vital Signs
- Weight
- Infusion

The following blood lab work will occur at this visit:

- Complete Metabolic Panel (CMP)
- Amylase
- Gamma-glutamyl transpeptidase (GGT)
- Complete Blood Count (CBC)/Differential
- Coagulation Measures
- Uric Acid
- Lactate dehydrogenase (LDH)
- C-reactive Protein (CRP)
- Creatine Kinase (CK)
- Cystatin C

The following urine lab work will occur at this visit:

- Urinalysis

9.5 Weeks 12 and 36 (Functional Assessment Visits) (+/- 1 week)

The following assessments will occur at this visit:

- Medical history
- Adverse Events
- Concomitant Medications
- Full Physical Exam
- Vital Signs
- Height
- Weight
- ECG
- Bayley scale of Infant Development (6 to 36 months of age)
- 100M – ambulant subjects (3.5 years until non-ambulant)
- NSAA (3 years to non-ambulant)
- Active-seated – non ambulant subjects (5 years and older)
- Pulmonary functional test (PFT) (10 years and older)

- Timed functional tests for (ambulant subjects 3 years and older)
- Pediatric Outcomes Data Collection Instruments (PODCI, ages 2-17)
- Patient-Reported Outcomes Measurement Information System (PROMIS) Upper Extremity Report (ages 18+)
- Infusion

The following blood lab work will occur at this visit:

- Complete Metabolic Panel (CMP)
- Amylase
- Gamma-glutamyl transpeptidase (GGT)
- Complete Blood Count (CBC)/Differential
- Coagulation Measures
- Uric Acid
- Lactate dehydrogenase (LDH)
- C-reactive Protein (CRP)
- Creatine Kinase (CK)
- Cystatin C

The following urine lab work will occur at this visit:

- Urinalysis

9.6 Weeks 16, 20, 28, 32, 40 and 44 (+/- 1 week)

The following assessments will occur at this visit:

- Medical history
- Adverse Events
- Concomitant Medications
- Brief Physical Exam
- Vital Signs
- Weight
- Infusion

9.7 Week 24 (Functional Assessment Visit) (+/- 1 week)

The following assessments will occur at this visit:

- Study drug infusion
- Medical history
- Adverse Events
- Concomitant Medications
- Full Physical Exam
- Vital Signs

- Height
- Weight
- ECHO
- ECG
- Bayley scale of Infant Development (6 to 36 months of age)
- 100M – ambulant subjects (3.5 years until non-ambulant)
- NSAA (3 years to non-ambulant)
- Active-seated – non ambulant subjects (5 years and older)
- Pulmonary functional test (PFT) (10 years and older)
- Timed functional tests for (ambulant subjects 3 years and older)
- Pediatric Outcomes Data Collection Instruments (PODCI, ages 2-17)
- Patient-Reported Outcomes Measurement Information System (PROMIS) Upper Extermity Report (ages 18+)

The following blood lab work will occur at this visit:

- Complete Metabolic Panel (CMP)
- Amylase
- Gamma-glutamyl transpeptidase (GGT)
- Complete Blood Count (CBC)/Differential
- Coagulation Measures
- Uric Acid
- Lactate dehydrogenase (LDH)
- C-reactive Protein (CRP)
- Creatine Kinase (CK)
- Cystatin C

The following urine lab work will occur at this visit:

- Urinalysis

9.8 Week 48 (or Early Termination Visit, if more than 28 days after a Functional Assessment Visit) (+/- 1 week)

Early termination assessments are the same as Week 48 assessments. An Early Termination visit is required if the patient discontinues more than 28 days after a Functional Assessment visit (Week 12, 24 or 36) The evaluations will take place over two visits.

9.8.1 Day 1

The following assessments will occur at this visit:

- Medical history
- Adverse Events

- Concomitant Medications
- Full Physical Exam
- Vital Signs
- Height
- Weight
- Infusion
- ECHO
- ECG
- Bayley scale of Infant Development (6 to 36 months of age)
- 100M – ambulant subjects (3.5 years until non-ambulant)
- NSAA (3 years to non-ambulant)
- Active-seated – non ambulant subjects (5 years and older)
- Pulmonary functional test (PFT) (10 years and older)
- Timed functional tests for (ambulant subjects 3 years and older)
- Pediatric Outcomes Data Collection Instruments (PODCI, ages 2-17)
- Patient-Reported Outcomes Measurement Information System (PROMIS) Upper Extremity Report (ages 18+)

The following blood lab work will occur at this visit:

- Complete Metabolic Panel (CMP)
- Amylase
- Gamma-glutamyl transpeptidase (GGT)
- Complete Blood Count (CBC)/Differential
- Coagulation Measures
- Uric Acid
- Lactate dehydrogenase (LDH)
- C-reactive Protein (CRP)
- Creatine Kinase (CK)
- Cystatin C

The following urine lab work will occur at this visit:

- Urinalysis

9.8.2 Day 2

A post-treatment open muscle biopsy will be performed in one gastrocnemius muscle. (Note that the rationale and methods of muscle biopsy site selection and performance for this and subsequent biopsies are discussed in Section 10.2.1). RNAseq analysis will be completed on tissue from this muscle biopsy.

Subjects should have the muscle biopsy performed following the Week 48 infusion and functional assessments. The biopsy at Week 48 must occur within 2 weeks after the Week 48 visit and at least 48 hours after the most recent infusion.

9.9 Schedule of Events

Table 6

TREATMENT WITH CASIRMERSEN, ETEPLIRSEN, OR GOLODIRSEN STUDY TIMELINE															
Study Period	Screening ^e		Baseline ^e (3-5 weeks after Screening)		Treatment Period										
Week #	Approximately 8 Weeks prior to Week 1		1 ^a	4	8	12	16	20	24	28	32	36	40	44	48/ ET ^{b,c}
Visit #	1	2	3	4	5	6	7	8	9	10	11	12	13	14	15
Informed consent/Assent ^f	X														
Assess Inclusion/Exclusion Criteria		X													
Confirm Eligibility			X												
Medical History	Continuous (Weekly)														
Adverse Events	Continuous (Weekly)														
Concomitant Medications	Continuous (Weekly)														
Study Treatment	Once Weekly ^g														
Port Placement		X ^f													
Muscle Biopsy		X													X ^h
RNAseq		X													X
Full Physical Exam	X	X	X	X		X			X			X			X
Brief Physical Exam					X		X	X		X	X		X	X	
Vital Signs ^c	X	X	Once Weekly												
Weight	X	X	X	X	X	X	X	X	X	X	X	X	X	X	X
Height		X	X			X				X		X			X
ECHO		X							X						X
ECG		X	X			X			X			X			X
Antibody testing Hep. B, C and HIV	X														
CMP	X	X	X	X	X	X			X			X			X
Amylase	X	X	X	X	X	X			X			X			X
GGT	X	X	X	X	X	X			X			X			X
CBC/Diff	X	X	X	X	X	X			X			X			X
Coagulations	X	X	X	X	X	X			X			X			X
Uric Acid	X	X	X	X	X	X			X			X			X
Lactate dehydrogenase (LDH)	X	X	X	X	X	X			X			X			X
C-reactive Protein (CRP)	X	X	X	X	X	X			X			X			X
Creatine Kinase (CK)	X	X	X	X	X	X			X			X			X
Cystatin C	X	X	X	X	X	X			X			X			X
Genotyping for DMD mutation, if not previously done	X														
Urinalysis	X	X	X	X	X	X			X			X			X
Bayley Scale of Infant Development		X	X			X			X			X			X
100 M		X	X			X			X			X			X
NSAA		X	X			X			X			X			X
Active Seated		X	X			X			X			X			X
Timed Function Tests		X	X			X			X			X			X
PFT		X	X			X			X			X			X
PODCI		X	X			X			X			X			X
PROMIS		X	X			X			X			X			X
	a. Week 1 should occur within 4 weeks of the Baseline Functional Assessment Visit. If the Week 1 visit is > 4 weeks after Baseline, the subject is required to repeat the Baseline functional assessments to reconfirm eligibility. b. Early termination assessments are the same as Week 48 assessments. An Early Termination visit is required if the patient discontinues more that 28 days after a Functional Assessment visit (Week 12, 24 or 36) c. During infusion visits, vitals will be measured approximately 30 minutes prior to infusion and approximately 5, 30, and 60 minutes after the end of the infusion. At all other visits, vitals will be measured only once. d. If there are changes to the study that affect the consent or assent, parents and or the subject will be reconsented/assented at their next visit. e. Visit will occur over multiple days f. A PORT will be placed per Principal Investigator discretion. g. All assessments that are to occur on the same day as an infusion will be completed prior to the infusion. h. The week 48 muscle biopsy must occur withing 2 weeks of the week 48 visit and at least 48 hours post the most recent infusion.														

9.10 Muscle and Strength Test Schedule

Table 7

	6 mos - 3 yrs	3 - 3.5 yrs	3.5 - 4.9 yrs	5 - 9.9 yrs	10 yr Until Non-Ambulant	Non-Ambulant
Bayley						
Timed Functional Tests						
NSAA						
100 meter						
ACTIVE						
PFTs						
Number of Assessments	1	3	3	4	5	3

10 STUDY PROCEDURES

10.1 Safety Assessments

10.1.1 Adverse Events

The collection of adverse events is described in Section 11.

10.1.2 Clinical Laboratory Evaluations

The following routine clinical laboratory tests will be performed at the time points specified in Section 9. Safety samples will be collected analyzed by an accredited central laboratory:

Hematology:	White blood cells (WBC), hemoglobin, hematocrit, platelets, red blood cells (RBCs), neutrophils, lymphocytes, monocytes, eosinophils, basophils, and any abnormal cells
Coagulation:	Prothrombin time, international normalized ratio (INR), and activated partial thromboplastin time (aPTT)
Chemistry:	Complete Metabolic Panel [CMP, including: sodium, potassium, chloride, carbon dioxide, blood urea nitrogen (BUN), creatinine, glucose, calcium, total protein, albumin, total bilirubin, alanine aminotransferase (ALT), aspartate aminotransferase (AST), and alkaline phosphatase], amylase, gamma-glutamyl transferase (GGT), uric acid, lactate dehydrogenase (LDH), C-reactive protein (CRP), creatine kinase (CK), and serum cystatin C
Immunology:	Hepatitis B, C and HIV
Urine:	Urinalysis (including: specific gravity, pH, cytology, hemoglobin, protein, glucose, and ketones)

** For subjects taking drugs that potentially induce GGT synthesis through the cytochrome P450 system, the clinically significant range will be estimated at two times the levels obtained from the baseline screening test.*

Any value outside of the current reference ranges for the laboratory performing the test will be flagged on the laboratory results. The Investigator will determine whether abnormal assessment results are clinically significant (CS) or not clinically significant (NCS). Clinical significance is defined as any variation in assessment results that has medical relevance resulting in an alteration in medical care. If clinically significant deterioration from Baseline levels is noted, the Investigator will continue to monitor the subject with additional assessments until:

- Values have reached normal range and/or Baseline levels

10.1.3 Electrocardiogram

Twelve-lead ECGs will be obtained at the time points specified in Section 9. ECGs will be performed at a consistent time of day throughout the study. ECGs will be performed only after the subject is in the supine position, resting, and quiet for a minimum of 15 minutes. The ECG will be manually reviewed and interpreted by medically qualified personnel according to pre-specified criteria. The Investigator will review the results and determine if the findings are clinically significant.

10.1.4 Echocardiogram

A standard 2-dimensional (2D) ECHO will be obtained at the time points specified in Section 9. ECHOs will be performed at a consistent time of day throughout the study. The ECHO will be reviewed and interpreted by medically qualified personnel according to pre-specified criteria. Ejection fraction (EF) will be noted. The Investigator will review the results of the ECHO report and determine if the findings are clinically significant.

10.1.5 Vital Signs, Weight, and Height

Vital signs (blood pressure, heart rate, respiration, and temperature) and weight will be measured at the time points specified in Section 9.

For infusion visits, vital signs are to be collected within approximately 30 minutes prior to infusion and approximately 5, 30, and 60 minutes after the end of the infusion. All assessments will be performed after subjects have remained seated for 5 minutes. Heart rate and respiratory rate are to be measured over 1 minute.

Temperature is to be recorded in degrees Celsius (°C).

Weight is to be recorded in kilograms. If a subject's weight varies by more than 10% from the prior visit, the subject is to be re-weighed to confirm the result, and an explanation of the change must be documented.

Height will be measured at the time points specified in Section 9. Height is to be measured with shoes off. If standing height cannot be obtained, height is to be calculated using the following equation³⁰:

$$\text{Height (cm)} = 4.605U + 1.308A + 28.003$$

where U is the length of the ulna in centimeters measured using an anthropometer or calipers, and A is the subject's age in years.

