6.3.2 Efficacy Endpoints

6.3.2.1 Primary Efficacy Endpoint

The primary efficacy endpoint is:

- Change from Baseline to Week 48 in dystrophin expression quantified by western blot in muscle biopsy tissue.

6.3.2.2 *Secondary Efficacy Endpoints*

Secondary efficacy endpoints are:

- Change from Baseline to Week 48 in expression of dystrophin as measured by immunofluorescent signal intensity and percent dystrophin positive fibers (PDPF) in muscle tissue sections in comparison to baseline values.
- The efficiency of splicing alteration will be measured by RNA Sequencing (RNA-Seq) to establish DMD mRNA copy number and the exon-exon junction frequency quantified, with normalization to exon junction read values from an exon junction in regions distinct from the targeted exon.

6.3.2.3 *Exploratory Efficacy Endpoints*

Exploratory efficacy endpoints are based on the change from Baseline to Week 48 in the following measures:

- Subjects 6 to 36 months of age at enrollment: Change from baseline in scores on the Bayley Scales of Infant Development – gross motor functions and fine motor functions.
- Change from Baseline to Week 48 in NSAA (subjects 3 years or greater).
- Change from Baseline to Week 48 on the 100M in ambulant subjects over the age of 3.5 years.
- Change from Baseline to Week 48 in ACTIVE-seated for boys over 5 years of age.
- Changes in FVC and FVC% predicted in patients aged ≥ 10 years.
- Peak expiratory flow as reported as % predicted by age and height (%PEF).
- Timed functional tests for ambulant subjects 3 years or older:
 - time to complete 10-meter run
 - time to rise from the floor
 - time to climb 4 steps
 - time to descend 4 steps
- Pediatric Outcomes Data Collection Instrument (PODCI) for patients ages 2-17.
- Adult Patient-Reported Outcomes Measurement Information System (PROMIS) Upper Extremity Report for patients 18+ years.
- Immune staining may be performed on biopsy specimens for members of the dystrophin-associated protein complex, such as the sarcoglycans, dystroglycans and n-Nos.
- Muscle morphometrics may also be performed, including fiber size histograms and quantification of central nucleation.

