7.2 Subject Inclusion Criteria

A subject must meet all of the following criteria to be eligible for this study.

1. Is a male with *DMD* and has an out-of-frame duplication of either exon 45, 51, or 53, with a normal copy number of all other *DMD* exons.
2. Is above age 6 months.
3. Has pulmonary function, that in the Investigator's opinion, is unlikely to decompensate significantly over the duration of the study.
4. Has sufficient muscle mass in a pair of bilateral muscles that will allow for pre- and post-treatment muscle biopsies per PI discretion.
5. If the subject is ambulant and 4 years old or greater and has been on a stable dose or dose equivalent of oral corticosteroids for at least 12 weeks prior to Week 1 the dose is expected to remain constant (except for modifications to accommodate changes in weight) throughout the study.

Note: Subjects are allowed to take other medications (excluding other RNA antisense or gene therapy agents) including angiotensin-converting enzyme (ACE) inhibitors, angiotensin receptor blocking agents (ARBs), β adrenergic blockers, potassium, and coenzyme Q, provided they have been on a stable dose for 12 weeks prior to Week 1. The dose is expected to remain constant throughout the study (modifications to doses to accommodate changes in weight are allowed).

6. Has (a) parent(s) or legal guardian(s) who is (are) able to understand and comply with all the study requirements.
7. Is willing to provide informed assent (if applicable) and has (a) parent(s) or legal guardian(s) who is (are) willing to provide written informed consent for the subject to participate in the study.

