14.4 Statistics

14.4.1 Disposition, Demographics, and Baseline Characteristics

The number and percentage of subjects completing or prematurely discontinuing the study will be summarized. Reasons for premature discontinuation will also be summarized.

Demographic characteristics including age (years), race, ethnicity, and Baseline characteristics including height (cm), weight (kg), and body mass index (kg/m²) will be summarized. Demographic data and Baseline characteristics will be presented in data listings.

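### The ulna-height equation in section 10.1.5 has no age limit, so a fully grown subject who cannot stand gains 1.308 cm of calculated height a year (minor)

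*Combined protocol and SAP*

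**What the plan says.** Section 10.1.5 makes the equation the rule for every subject who cannot be measured standing: "If standing height cannot be obtained, height is to be calculated using the following equation". The formula is "4.605U + 1.308A + 28.003", where U is ulna length "and A is the subject's age in years". The section gives no age range, no cap, no adult alternative, and no choice between decimal and completed years.

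On who may need it:

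- The only age criterion in section 7.2 is "Is above age 6 months".
- Section 6.3.2.3 includes a PROMIS "Upper Extremity Report for patients 18+ years".
- The visit lists schedule "Active-seated – non ambulant subjects (5 years and older").
- Section 4.1 says that most boys depend on a wheelchair by 10 to 14 years of age.

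On where height is used:

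- Section 6.3.2.3 lists "Peak expiratory flow as reported as % predicted by age and height (%PEF") and change in FVC% predicted from age 10. No reference equation is named for either.
- Section 14.3.2.1 tabulates height by visit with change from Baseline.
- Section 14.4.1 summarizes "Baseline characteristics including height (cm), weight (kg), and body mass index".

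**The concern.** The formula has one term for bone length and one for age. In a growing child both rise. In a skeletally mature adult the ulna is fixed but age is not, so the formula reports growth that is not happening. Measuring the same way at every visit does not cure this, because the error comes from A and not from a switch between standing and ulna height.

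Too great a height raises the predicted lung volume and so lowers the percent-predicted value. An affected adult would look worse at Baseline and would show a small built-in decline. Section 5.3 sets the functional measures, FVC% among them, against expected natural history, so the error would work against the study drug. With six subjects spread over three drugs, one affected adult could be a large share of a treatment group's summary.

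**Working it through.** The plan states no figure that depends on this point, so there is nothing of its own to reproduce. The equation can be evaluated directly.

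**Inputs from the protocol.** The coefficients are 4.605, 1.308 and 28.003 (10.1.5). Week 1 falls within 4 weeks of Baseline (9.2) and Week 48 has a window of 1 week either way (9.8), so about 47 to 52 weeks separate the two heights.

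**Assumptions, not in the documents.** Ulna length is 26 cm and constant (24 cm as a check). The age term is held at 18 as the comparison, and at 16 to 20 as a range. Predicted lung volume scales with height to the power k, with k from 1 to 3. FVC% is 50.

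**Drift within the study.** With U fixed, height changes by 1.308 cm per year of age.

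- 47 weeks: 1.308 × 47 × 7/365.25 = 1.18 cm
- 48 weeks: 1.308 × 48 × 7/365.25 = 1.20 cm
- 52 weeks: 1.308 × 52 × 7/365.25 = 1.30 cm

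If A means completed years, the drift becomes a single step of 1.308 cm at a birthday.

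The false change in FVC% is 50 × [(H/(H + drift))^k − 1]. For 48 weeks and U = 26:

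- Age 18, H = 171.28: −0.35 at k = 1 and −1.04 at k = 3
- Age 30, H = 186.97: −0.32 at k = 1 and −0.95 at k = 3

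That is about 0.3 to 1.0 points. The extreme corner (52 weeks, U = 24, age 18, k = 3) reaches −1.19.

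**Level error.** For U = 26 the fixed part is 4.605 × 26 + 28.003 = 147.733 cm. Adding 1.308 × A gives the calculated height, and r is its ratio to the height with A held at 18. The BMI error is r^−2 − 1, and a true FVC% of 50 reads as 50 × r^−k.

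| Age | Height (cm) | Excess over A = 18 (cm) | r | BMI error | FVC% of 50 reads, k = 1 to 3 |
|---|---|---|---|---|---|
| 18 | 171.3 | 0 | 1 | 0 | 50 |
| 20 | 173.9 | 2.6 | 1.0153 | −3.0% | 49.2 to 47.8 |
| 25 | 180.4 | 9.2 | 1.0535 | −9.9% | 47.5 to 42.8 |
| 30 | 187.0 | 15.7 | 1.0916 | −16.1% | 45.8 to 38.4 |

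The excess in centimetres does not depend on U. It does depend on where growth is taken to end:

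- Age 25: 1.308 × (25 − 20) = 6.5 cm to 1.308 × (25 − 16) = 11.8 cm
- Age 30: 1.308 × (30 − 20) = 13.1 cm to 1.308 × (30 − 16) = 18.3 cm

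**The case against.** The case for leaving this alone is that nothing of weight depends on it, and most of that case stands.

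- **Reach.** FVC% and %PEF are exploratory, and section 14.3.1.3 says only that listings and descriptive summaries may be provided. BMI is a Baseline descriptor. The primary endpoint is western blot, dosing uses weight (8.2), and the continuation threshold uses dystrophin-positive fibers (14.3.1.2). Absolute FVC, already an endpoint, does not use height.
- **Who is affected.** A reader might infer that adults are expected to enrol. The documents show only that adults are allowed for. Inclusion criteria 6 and 7 are written around parents or guardians, and criteria 3 and 4 ask for stable pulmonary function and enough muscle for two biopsies. Among six subjects, possibly none is a grown adult who cannot stand.
- **Ages.** The errors at 25 and 30 catch the eye, but section 4.1 puts historical death in the late teens or early 20s, with newer care adding perhaps several years. At 20 the excess is 2.6 cm.
- **Change scores.** A reader might infer that affected adults would appear to decline materially faster. A drift of 1.20 cm equals an ulna misreading of 1.20/4.605 = 0.26 cm and moves FVC% by about 1 point at most, which is little in a descriptive listing.

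These points set the priority. They do not make the rule right. It is mandatory as written, nothing elsewhere limits the age term, and a subject to whom it gives a wrong height is eligible and foreseen.

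**Conclusion.** The equation as written gives a wrong height for a skeletally mature subject who cannot stand. That follows from its form and needs only the assumption that the adult ulna is constant. The drift is 1.308 cm a year, about 1.2 to 1.3 cm over the study, and using one method throughout does not remove it.

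The size of the level error is less certain. The 2.6, 9.2 and 15.7 cm at ages 20, 25 and 30 take the equation's value at 18 as the reference. A reader might treat that value as the subject's true height, or 18 as the validated limit of the equation. The documents support neither, since they do not give the age range of the data behind it. The FVC% figures need two further assumptions: that its reference equation uses height, which is stated only for %PEF, and that k lies between 1 and 3.

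A reader might also infer a threat to the efficacy conclusion. There is none: the western blot endpoint, weight-based dosing and absolute FVC are untouched. This is a minor correction to exploratory and descriptive outputs, needed only if such a subject enrols.

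**What to change.** Add two sentences to section 10.1.5:

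1. Define A as the smaller of the subject's age and a stated cap, and say whether age is in decimal or completed years. Eighteen years is a working assumption for the cap. The sponsor should confirm it, or use the upper age limit of the data behind the cited equation if that is lower.
2. For subjects at or above the cap at Baseline, use Baseline height at all visits for FVC% predicted and %PEF.

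Show absolute FVC beside the percent-predicted values. A subject who reaches the cap during the study is covered by the first sentence, because his age term then stops rising.

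The cost is the two sentences and one check of the cited source, with no new measurement. Two limits remain. Capping A stops the drift but does not show that height at the cap is correct. Fixing Baseline height also ignores any real growth after the cap.
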